4.4 HYPOXIA AND [^{18}F] FLUOROMISONIDAZOLE (^{18}F -MISO) PET

Hypoxia has been demonstrated in solid tumors and has been shown to be associated with resistance to chemotherapy, as well as potentially contributing to a more aggressive and invasive phenotype. One of the key players thought to orchestrate these changes is hypoxia inducible factor 1-alpha (HIF1- α), which acts as a transcription factor inducing production of numerous proteins that alter microenvironment and promote growth, neoangiogenesis, and invasion. Yang et al investigated HIF1- α expression in osteogenic sarcoma, and noted that 80% of tumors expressed HIF1- α , with increased microvessel density, a marker for hypoxia and likely resultant angiogenesis within tumor tissue (18). [^{18}F]-MISO PET scanning has been described in the literature as a tool to measure hypoxic areas in tumors (19). [^{18}F]-MISO accumulates in viable tissues preferentially when $\text{pO}_2 < 10$ mmHg and is dependent on nitroreductase activity within the cell. It is not dependent on blood flow, and is not retained in necrotic tissue. Studies have demonstrated changing hypoxia status in irradiated non-small cell lung cancer using this modality, as well as several papers in soft tissue sarcoma and head and neck cancers (20-24).

In our previous work, we demonstrated that changes in SUVmax measured by traditional FDG-PET scanning did not correlate with response to therapy. This suggests that FDG-PET may underestimate treatment response, possibly due to post-therapy inflammatory changes. Our interest in using [^{18}F]-MISO PET is two-fold. Our main question is whether tumors with higher [^{18}F]-MISO PET indices prior to treatment (increased hypoxia) might display less response to our proposed radiation therapy, which might ultimately allow us to predict patients likely to benefit. We also will investigate whether an *improvement* in oxygenation status (decrease in [^{18}F]-MISO indices) following treatment might correlate with histologic response to therapy given the lack of uptake demonstrated in necrotic tissue. In an effort to improve sensitivity of the [^{18}F]-MISO assessment of hypoxia and ensure attention to tumor volumes, we will combine the imaging with traditional [^{18}F]-FDG PET.

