6.2.4. Acquisition of [^{18}F]-MISO/ [^{18}F]-FDG PET *imaging*

We plan to obtain investigational imaging of tumor hypoxia using [^{18}F]-MISO in combination with traditional [^{18}F]-FDG PET imaging. Following treatment, we will analyze the [^{18}F]-MISO PET data to determine any correlation to clinical response defined by traditional RECIST criteria with CT/MRI imaging, and percent necrosis as determined by histology as detailed in section 10.1.

Protocol: Patients will undergo FDG-PET/CT according to standard protocols, and [^{18}F]-MISO PET scanning as per the described protocol (21). Images will be compared side-by-side to ensure accurate inclusion of tumor fields, as described by Rajendran (23). Four venous blood samples will be collected five minutes apart to normalize Tumor/Blood ratios as described in reference 23. Additionally, ratios between tumor and contralateral soft tissue, as well as tumor/adjacent muscle will be obtained. Ratios of greater than 1.2 will be considered hypoxic. Ratios will be converted to milliliter volume to measure hypoxic tumor volume. We will discount any lesions occurring in the liver or bladder from study due to inaccurate readings previously reported.

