11.0 STATISTICAL CONSIDERATIONS

11.1 OVERVIEW

This protocol will assess the proportion of clinical tumor responses, defined as progression-free survival at 6 months, and the toxicities associated with high-dose ^{153}Sm -EDTMP (MTD at 30 mCi/kg) after an initial lower dose of the agent along with external beam radiation therapy in patients with high-risk osteogenic sarcoma.

Primary objective: The primary objective of this study is to determine if the addition of external beam radiation therapy to infusional ^{153}Sm -EDTMP can delay the progression of target lesions. The primary endpoint is 6-month progression free survival (PFS). It is a combined effect of the entire treatment. To be evaluable, patients must meet all eligibility criteria, including signing a consent form, and have completed treatment according to protocol without major deviations. Patients who are enrolled but unevaluable will be replaced on the study. Only patients enrolled on Stratum 1 (i.e., with a diagnosis of osteosarcoma) will be evaluated for the Primary Objective.

Secondary objectives:

1. Describe the short and long-term toxicity profile of combined treatment with ^{153}Sm -EDTMP and external beam radiation therapy.
2. Estimate the local control rate. (Stratum 1 only)
3. Determine the overall survival (OS). (Stratum 1 only)
4. Describe the distribution of absorbed doses delivered to each targeted lesion and the distribution of equivalent uniform doses delivered to each patient.
5. Model the relationship between absorbed doses and time to progression.
6. Determine the correlation of hypoxic volume and maximum tumor/blood ratio obtained by [^{18}F]-MISO PET scanning with patient outcomes.

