Toxicities will be graded according to CTCAE v4.0 and the RTOG Cooperative Group Common Toxicity Criteria, and attributable toxicities grade 3 or higher will be recorded. For purposes of evaluation, we will consider toxicities resulting from the administration of ¹⁵³Sm-EDTMP separately from toxicities resulting after initiation of external beam radiation therapy. [However, we will hold accrual after enrollment of five patients to evaluate cumulative toxicity from the combined regimen.] Adjustments to external beam therapy in response to toxicity would be made in accordance with standard Radiation Oncology treatment protocols and clinical judgment.

11.3.3 Describe the distribution of absorbed doses delivered to each targeted lesion and the distribution of equivalent uniform doses delivered to each patient.

The total absorbed dose delivered to each targeted lesion will be limited by the tolerance of surrounding normal tissue. We will produce histograms showing the distribution of radiation absorbed doses by lesion, and summarize the results by patient for the lesion receiving the lowest absorbed dose in each patient. With a sample size of 20 patients, we will be able to estimate the proportion of patients whose lesions are all treated to an absorbed dose of ≥ 80 Gy with a precision of $\pm 23\%$.

11.3.4 Model the relationship between absorbed dose and time to progression for patients enrolled in Stratum 1.

We expect a total dose of 80 to 100 Gy to produce a local control rate of 80%, while a total absorbed dose of 60 to 70 Gy may produce a local control rate of 50 – 70%, and the local control rate would decline steeply at lower absorbed doses. We will use a generalized mixed effects model treating dose and time as fixed effects and the random effect of individual patients for the outcome of progression of each targeted lesion. If at least 10 patients have at least one lesion that receives a radiation dose with similar effectiveness to our historical control experience, and at least one lesion receiving the targeted dose, this analysis would have 80% power to demonstrate a significant dose-response with alpha 0.05.

11.3.5 Determine overall and progression-free survival for patients enrolled in Stratum 1.

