Survival curves will be estimated by using the Kaplan-Meier method. Progression-free survival is defined as time from registration to the first observation (documentation) of disease progression or death. Patients who are lost to follow-up will be censored for determination of PFS on the date of their last evaluations. Overall survival is defined as time from registration to death due to any cause.

11.3.6 Determine correlation of hypoxic volume and maximum tumor/blood ratio obtained by [¹⁸F]-MISO PET scanning with patient outcomes.

Cox regression analysis will be performed to measure association between hypoxia based on HV and max T/B ratio with Kaplan-Meier survival and time-to-progression curves. Additional regression analysis will be performed to evaluate the link between hypoxic indices and uptake of ¹⁵³Sm-EDTMP and clinical response based on radiologic response and presence of necrosis on histology.

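### Section 4.4 asks whether more hypoxic tumours respond less, but 11.3.6 relates hypoxia to patient-level outcomes, gives no rule for several lesions and has no lesion-level progression model, although 11.3.4 plans one for dose

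*Combined protocol and SAP*

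**What the plan says.** Section 4.4 states the question by tumour: "Our main question is whether tumors with higher [^{18}F]-MISO PET indices prior to treatment (increased hypoxia) might display less response". The same sentence adds the hope of eventually predicting which patients benefit. Secondary objective 6 in 11.1 moves to the patient: "Determine the correlation of hypoxic volume and maximum tumor/blood ratio obtained by [^{18}F]-MISO PET scanning with patient outcomes".

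The analysis is in 11.3.6: "Cox regression analysis will be performed to measure association between hypoxia based on HV and max T/B ratio with Kaplan-Meier survival and time-to-progression curves". A second sentence begins "Additional regression analysis will be performed to evaluate the link between hypoxic indices and uptake of" the samarium compound and goes on to clinical response from imaging and necrosis. Neither sentence gives a unit of analysis, an effect size, an alpha level or a number of events.

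The time-to-event outcomes are patient-level. Under 11.3.5, "Progression-free survival is defined as time from registration to the first observation (documentation) of disease progression or death". Time to progression has no separate definition.

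Other sections work by lesion. Section 11.2 intends every lesion visible at enrolment to be a target lesion in Stratum 1. Section 6.2.4 handles the hypoxia scan by lesion: "We will discount any lesions occurring in the liver or bladder from study due to inaccurate readings previously reported". For absorbed dose, 11.3.4 plans a mixed model with "the random effect of individual patients for the outcome of progression of each targeted lesion".

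**The concern.** The question concerns tumours, and the planned time-to-event outcomes belong to patients. A patient with several lesions has several hypoxia readings but one time to first progression, and 11.3.6 does not say how the two are joined.

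There are two readings, and each has a fault.

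- **One value per patient.** This is the likelier reading, given objective 6 and the survival outcomes. The most hypoxic lesion may be stable while a well-oxygenated one progresses, and the data row looks the same as if the hypoxic lesion had failed. A liver lesion left out of the hypoxia measure could still supply the patient's event. So could a new lesion, which has no baseline scan value but counts as progression under 9.1.1.5.
- **Several lesions per patient.** The Cox model as written has no cluster term or random effect, so correlated lesions would be treated as independent.

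At stake is whether the trial can speak to what 4.4 calls its main hypoxia question. Absorbed dose also varies by lesion, and 11.3.4 expects local control to vary strongly with it. Only a lesion-level model can set a lesion's hypoxia beside that lesion's own dose.

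**Working it through.** **1. The nearest figure the plan states.** Section 11.3.6 gives no power. Section 11.3.1 gives 82% for the primary test (20 patients, one-sided 0.05, hazard ratio 1.76). The hazards are -ln(0.158)/6 = 0.3075 and -ln(0.35)/6 = 0.1750 per month, ratio 1.758. With 20 events, the exact exponential test has power P(χ²₄₀ > 55.76/1.758) = P(χ²₄₀ > 31.7) = 82.3%. The log-hazard approximation gives about 81%. The plan's figure reproduces, but it says nothing about the hypoxia analysis.

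**2. What a patient-level Cox model can detect.** For a continuous covariate with d events, at 80% power and two-sided 0.05, the detectable hazard ratio per SD is exp[(1.960 + 0.842)/√d].

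- d = 20: exp(2.802/4.472) = 1.87
- d = 18: exp(2.802/4.243) = 1.94
- d = 15: exp(2.802/3.873) = 2.06

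Only large effects are within reach.

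**3. Patient level against lesion level, by simulation.** From the documents: 20 patients, and a total hazard set near the 35% target for 6-month PFS. Assumed, because the documents give no figure: hazard ratio 2 per SD of a normally distributed lesion hypoxia score; equal lesions per patient; the within-patient correlation of hypoxia shown in the table; patient frailty variance 0.5 on the log hazard unless noted; death at 0.02 per month, treated as censoring. The patient-level model regresses time to first progression on the highest lesion score. The lesion-level model is a Cox model with patient-clustered standard errors. Both use critical values calibrated to two-sided 5% (1000 runs). Power comes from 500 runs per setting, with an error of about 2 points.

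| Lesions per patient | Correlation | Follow-up of lesions | Patient-level power | Lesion-level power |
|---|---|---|---|---|
| 1 | n/a | all | 49% | 43% |
| 3 | 0.9 | all | 46% | 62% |
| 3 | 0.5 | all | 36% | 79% |
| 3 | 0.2 | all | 30% | 84% |
| 5 | 0.2 | all | 19% | 90% |
| 3 | 0.9 | to patient's first progression | 46% | 46% |
| 3 | 0.5 | to patient's first progression | 36% | 58% |
| 3 | 0.9, frailty variance 1.5 | all | 27% | 31% |

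As a share of the lesion-level power, the patient-level model loses 1 - 46/62 = 26% in the second row, 1 - 36/79 = 54% in the third and 1 - 19/90 = 79% in the fifth. It loses nothing with one lesion per patient. With three lesions and correlation 0.9, it loses nothing if follow-up of lesions stops at the patient's first progression.

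**4. Size of the lesion-level test.** Against ordinary critical values at nominal 5%, the clustered standard error rejected mostly 6-9% of the time under no effect. With about 20 clusters it is too liberal unless corrected.

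**The case against.** Four points carry weight.

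First, 11.3.6 does not say that each patient contributes one ratio and one volume. A reader might infer that the plan chose to collapse the lesions. The text supports only that the unit and the summary rule are unstated.

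Second, a patient-level analysis is legitimate for part of the aim. Section 4.4 looks ahead to predicting which patients benefit, objective 6 names patient outcomes, and the patient is the right unit for overall survival.

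Third, the second sentence of 11.3.6 could be run by lesion in part: uptake is mapped by lesion, and necrosis is recorded for resected lesions (6.3.7). It does not fill the gap. Uptake is not response, histology will exist only for some patients (6.2), and clinical response is defined per patient in 9.1.3, although 6.2 does speak of response of tumour lesions. None of these outcomes is time to progression of a lesion.

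Fourth, lesion-level follow-up is not assured. Scheduled CT/MRI covers the primary tumour and any large metastases (footnotes to both schedule tables). Continued observation of stable lesions after one progresses is an intention tied to optional local therapy (6.2). Target lesions are pre-specified only for Stratum 1, while the hypoxia objective is not restricted to it. The exclusion of liver and bladder lesions in 6.2.4 could also mean exclusion from outcome as well as predictor, but the text does not settle this.

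**Conclusion.** The mismatch stands on the text alone: a question about tumours, patient-level time-to-event outcomes, no stated unit or summary rule, and no lesion-level progression model for hypoxia where 11.3.4 has one for dose. Section 11.3.6 needs repair on either reading.

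A reader might go further and conclude that the planned analysis throws away most of its power. The documents do not support that. They give no lesion count per patient, no within-patient correlation of hypoxia and no between-patient variation in risk, and they do not guarantee follow-up of lesions after a first progression. Under the assumed values the gain runs from none to large. It exceeds half of the lesion-level power with three or more lesions, correlation of 0.5 or less, frailty variance 0.5 and every lesion followed. It is modest or absent when lesions within a patient are alike, when frailty is strong as well, or when there is only one lesion.

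This is a worthwhile, inexpensive improvement to a secondary objective. It does not affect the primary endpoint.

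**What to change.** In 11.3.6:

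- Add, for Stratum 1 target lesions, an exploratory lesion-level model of time to progression on each lesion's own pre-treatment tumour/blood ratio and hypoxic volume, with patient as a random effect as in 11.3.4.
- Include the lesion's absorbed dose as a covariate where the number of events allows.
- Use a small-sample correction or a permutation test, because of the 6-9% size found above.
- Use the same lesions for predictor and outcome: liver and bladder lesions out of both, and new lesions not counted as lesion-level events because they have no baseline value.
- State how hypoxic volume and maximum ratio are summarised per patient, for example total or largest volume, and maximum over which lesions.
- Keep the patient-level Cox model for overall and progression-free survival.

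The cost is SAP wording and a little more analysis; no change to the planned scans or sample size is proposed. The main weakness is that lesion-level follow-up may be incomplete after a patient's first progression, so the report should say how many lesions were followed beyond it.

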6.2.5 Planning and administration of external beam radiation therapy

Initial planning CTs for radiation therapy will be performed just prior to initiation of therapy. After each samarium infusion, if tolerable, the patient will be placed in a reproducible treatment position using an appropriate immobilization device based on treatment site while data from SPECT/CT is obtained. Alternatively, the two CT

components will be co-registered and combined fields generated. Subsequent radiation therapy will be planned to reach a total minimum dose to tumor of 75 Gy as described (25). The dose of supplemental EBRT will be decided after determination of the EBRT dose equivalent delivered by the ^{153}Sm in order to reach a total minimum dose to the gross tumor volume (GTV) of 75 Gy. GTV will be defined as gross tumor on the two planning CT scans. A margin of 1.5 cm will be added to the GTV to create a clinical target volume (CTV) which will be modified to exclude adjacent normal tissues that are not involved by tumor. An additional margin of 5 mm-1 cm will be placed around the CTV to create a planning target volume (PTV) and will be dependent on treatment site and immobilization technique.

Conformal techniques such as intensity-modulated radiotherapy (IMRT) or tomotherapy will be used to plan the supplemental EBRT. The goal will be to achieve a target supplemental EBRT dose coverage of $D_{95} > 95\%$ to the PTV. Normal tissue dose constraints based on QUANTEC will be applied and respected. Standard protocols apply for supportive care based on site irradiated, and toxicity will be closely documented.

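### Section 11.3.6 treats hypoxic volume in millilitres as a measure of hypoxia with no tumour-volume term, so an association with outcome may reflect tumour burden

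*Combined protocol and SAP*

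**What the plan says.** Section 6.2.4 sets the hypoxia threshold, "Ratios of greater than 1.2 will be considered hypoxic", and then states: "Ratios will be converted to milliliter volume to measure hypoxic tumor volume". It does not divide by tumour volume, and it leaves liver and bladder lesions out of the hypoxia reading.

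Section 11.3.6 then plans Cox regression to measure the "association between hypoxia based on HV and max T/B ratio" with survival and time-to-progression curves. It names no covariate, scaling or transformation. The same indices are reused: "Additional regression analysis will be performed to evaluate the link between hypoxic indices and uptake" of the samarium agent, and also clinical response.

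Section 4.4 gives the question behind this, namely whether "tumors with higher [^{18}F]-MISO PET indices prior to treatment (increased hypoxia) might display less response to our proposed radiation therapy". Section 11.2 intends every lesion visible at enrolment to be a target and counts the first progression at any of them, or death, as the event.

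Tumour volume can be obtained from planned images. Section 4.4 pairs the hypoxia scan with FDG-PET partly to "ensure attention to tumor volumes", and 6.2.5 states: "GTV will be defined as gross tumor on the two planning CT scans". No section lists total tumour volume as an analysis variable.

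**The concern.** The question is about oxygenation, but HV also rises with the amount of tumour. Two patients with the same hypoxic fraction have different HV if one has more or larger lesions. With a first-progression-at-any-lesion endpoint, the patient with more lesions also has more chances of an event. A Cox model with HV and no volume term cannot separate more hypoxia from more tumour.

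Two errors are possible. Burden could be reported as a hypoxia effect and later cited when predicting who benefits, which 4.4 names as a possible eventual use. Or variation in tumour volume could bury a real effect of hypoxic fraction.

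**Working it through.** **The plan's own figure.** Section 11.3.6 states none. The figure that bears on it is the 82% power in 11.3.1, because it fixes the number of events.
- Hazards: -ln(0.158)/6 = 0.3075 and -ln(0.35)/6 = 0.1750 per month; ratio 1.758 (plan: 1.76).
- With 60 months of accrual, 12 more of follow-up and hazard h = 0.1750, P(event) = 1 - [exp(-12h) - exp(-72h)]/(60h) = 0.988, so 20 x 0.988 = 19.8 events.
- The exact one-sided 0.05 exponential test has power 81.8% (82.2% with 20 events). The plan's 82% reproduces. The Cox models will have about 20 events.

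**Structure of HV.** Write V for tumour volume and F for hypoxic fraction. HV = V x F, so log HV = log V + log F. Let R2 be the share of log HV variance explained by log V. The documents give no spread for V or F, so R2 is varied.

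**False signal when only volume matters.** Assumptions: n = 20, log-normal V (SD of log V 0.3 to 1.2), logit-normal F with median 0.2 (SD of logit 0.5 to 1.2), F without effect; 4,000 trials per setting, two-sided 0.05 Wald test. The plan names no transformation, so both scales are shown. Percentage of trials significant for HV alone:

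| R2 | log HV, volume HR 1.5 per SD | log HV, HR 2.0 | untransformed HV, HR 1.5 | untransformed HV, HR 2.0 |
|---|---|---|---|---|
| 0.90 | 29.9 | 63.9 | 30.2 | 59.1 |
| 0.62 | 21.4 | 44.0 | 23.4 | 46.3 |
| about 0.32 | 12.0 | 22.2 | 18.5 | 29.5 |
| 0.13 | 6.8 | 9.0 | 10.2 | 15.1 |

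In the same settings, log HV adjusted for log V is significant in 5.7-6.8% and hypoxic fraction alone in 5.1-5.8%. If volume is not prognostic, log HV alone is significant in 5.2-5.9%.

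**False signal from lesion count alone.** With k lesions at equal, independent hazard h, the hazard of first progression is k x h. Here neither lesion size nor F affects outcome (lesion volume log-normal with SD of log 1, F Beta(2,4), HV summed per patient, 3,000 trials per setting). Log HV alone is significant in 12-14% with 1-3 lesions, 23-28% with 1-6 and 33-41% with 1-10. Adjusted for log V it is 6-7%; fraction alone gives 5-8%. The lesion counts and the summing are assumptions.

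**Missed signal.** If F matters (HR 2.0 per SD) and V does not, power for log HV alone is 10%, 28% or 48% at R2 of 0.90, 0.62 or 0.31. It is 64-69% for HV adjusted for log V, or for the fraction.

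**Fraction correlated with volume.** With correlation 0.4 and only V prognostic (HR 2.0), log HV alone is significant in 54%, fraction alone in 12%, and HV adjusted for log V in 6.0%.

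**Cost of adjusting.** The detectable HR per SD of HV (80% power, two-sided 0.05) is exp{(1.960 + 0.842)/sqrt[19.8 x (1 - R2)]}: 1.88 at R2 = 0, 2.44 at 0.5, 4.09 at 0.8 and 7.34 at 0.9. Two remarks:
- b1 log HV + b2 log V = b1 log F + (b1 + b2) log V. Adjusting log HV for log V is therefore the same model as log fraction with log V. The widening is per SD of HV; power for a true fraction effect stayed at 64-69%.
- The formula is optimistic at this size. For HR 2.0 and 19.3 events it implies Phi(sqrt(19.3) x ln 2 - 1.96) = Phi(1.09), or 86%.

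**The case against.** The strongest reply is that the size of the problem is unknown. A reader might infer that HV is mostly tumour volume and that the Cox analysis will report burden as hypoxia. The documents support neither statement. They give no distribution of tumour volume or hypoxic fraction and no hazard ratio for volume. Their only direct remark linking size to response is the canine finding in 4.2, where large size is mixed with minimal bone formation. That stands, and it is why the result is a range. The lesion-count argument rests on the endpoint in 11.2, but it still needs assumed lesion numbers.

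The maximum tumour/blood ratio is planned beside HV and is not a volume. A result seen for HV but not for the ratio would warn a careful reader. This is a partial safeguard, but it does not give HV the interpretation intended. Section 11.3.6 also sets no alpha or selection rule; it only measures association.

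Hypoxic fraction is not a complete remedy. It fails if fraction correlates with volume (12% above). Section 4.4 also says the tracer is not retained in necrotic tissue, so a necrotic lesion contoured on CT could score a low fraction. This stands, and it favours keeping log volume in the model.

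A reader might also infer that both strata share one baseline hazard, because 11.3.6 names no stratum. The documents do not say so. Sections 3.2.5 and 11.3.5 and secondary objective 3 in 11.1 assign survival outcomes to Stratum 1. A missing label is weak evidence: secondary objective 5 has none either, yet 11.3.4 restricts it to Stratum 1.

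**Conclusion.** The point holds as a possible bias. HV is an absolute volume used as a measure of hypoxia, the plan has no volume term, and the endpoint lets burden raise both HV and the hazard. With about 20 events, unadjusted log HV would be falsely significant in about 7-64% of trials if volume has a hazard ratio of 1.5-2.0 per SD and volume explains 13-90% of log HV variance. There is no inflation if burden is not prognostic. All spreads and effects are assumptions. Only the HV half of the analysis is directly affected. This is a cheap improvement to a secondary analysis; the primary endpoint, its power and the stopping rules are untouched.

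**What to change.** In 11.3.6, add log total tumour volume to each model containing HV, or use hypoxic fraction (HV divided by total tumour volume) as the index with log total tumour volume as covariate. Report this beside the unadjusted HV result. State three details:
- One source of tumour volume, either the planned FDG-PET/CT or the GTV contours, listed as a variable to be recorded.
- HV and tumour volume measured over the same lesions, with liver and bladder lesions excluded from both.
- The scale of HV. If a patient may have no tissue above the threshold, log HV is undefined, and the fraction on its natural scale avoids this.

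At most, add one line saying that the Cox models for survival and progression are restricted to Stratum 1, as in 11.3.5.

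The cost is SAP wording, measurement of total tumour volume from images already planned, and one more covariate with about 20 events. The interval for HV will widen when HV and volume are collinear.
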